The primary analysis is a logistic regression with treatment arm as a predictor. For the primary analysis, we propose to use study site as a *random effect* (random intercept model). The null hypothesis is that the regression coefficient for treatment arm equals zero, which will be tested using a likelihood ratio test with one degree of freedom. We will also fit the following models: (a) a model including drug, site, and drug \times site interaction, (b) a model including only drug and site, (c) a model including only drug and country, and (d) a model with drug, country, drug-country interaction, and site within country. Countries or sites with fewer than three observations will be pooled together. Provided there is no evidence of treatment \times site interaction or treatment \times country interaction, we will report pooled treatment effects and confidence intervals. In the event evidence suggests a difference between treatment sites, we will report treatment effects by site, and repeat the analysis excluding particular sites. Similarly, evidence of a treatment \times country interaction will lead us to report treatment effects and confidence intervals by country.

Simulations suggest that use of a model containing interaction terms between site or country and treatment for the primary analysis is undesirable. Such a procedure results in modest loss of power unless the treatment effect is of opposite sign in different sites or countries.

The hypothesis test is to be two-sided with alpha of 0.05. We propose to compute the P-value by permutation testing, based on the block randomization scheme.

Prespecified Subgroup Analysis.

The prespecified subgroup analysis will test the hypothesis that there is a treatment effect separately in each anatomic group, using a logistic regression model.

We denote the two anatomic groups by X_i^3 , which equals 0 when the patient is in the intermediate group and 1 when the patient is in the posterior/pan group. In the intermediate subgroup, we plan to determine whether there is evidence of a treatment effect (regardless of the effect in the posterior/pan group). Specifically, we will conduct this analysis in two ways: anatomical site at enrollment (split into three categories: anterior, anterior/intermediate or intermediate only, and posterior/panuveitis), and anatomical location by history (split into two

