3.4 Sample Size Evaluation

3.4.1 Primary Calculation

The sample size for the trial will be 216 subjects, which we anticipate will provide approximately 80% power to detect a difference of 20% in the proportion of patients achieving control of inflammation at six months between the methotrexate and mycophenolate mofetil groups.

This sample size was determined based on the primary objective (superiority comparison of mycophenolate mofetil to methotrexate) and primary endpoint (treatment success). We assumed an effect size of 20%, as this was deemed to be clinically meaningful, and well within the distribution of the investigators' prior beliefs from published retrospective studies.

An approximate sample size is provided by the formula

$$2N = \frac{4(Z_{\alpha} + Z_{\beta})^2 \bar{p}(1-\bar{p})}{(p_c - p_i)^2} \quad (5)$$

(see Friedman et al. 2010), where α is the significance level (0.05, two sided), β is one minus the power (the desired power is 80%), p_c is in this case the probability of success in the methotrexate group (we estimate this at 0.4), p_i is the probability of success in the mycophenolate mofetil group (we estimate this at 0.6), and \bar{p} is $\frac{1}{2}(p_i+p_c)$. We assume 10% will be lost to follow-up in the first six months; details are given in the full proposal. This yields approximately 108 patients in each of the two groups, for a total of $2 \times 108 = 216$ subjects.

A power table is provided below as a sensitivity analysis (to show how the detectable effect size changes with varying success rates).

Success rate with Drug A	80% Power		90% Power	
	Detectable effect size	Success rate with Drug B	Detectable effect size	Success rate with Drug B
20%	18%	38%	21%	41%
30%	20%	50%	23%	53%
40%	20%	60%	23%	63%
50%	20%	70%	22%	72%
60%	19%	79%	21%	81%

Simulation confirms that this method yields adequate sample sizes for the logistic regression (results not shown).

Note that for the final analysis, the critical value will be adjusted slightly because of the interim analysis.

Sample size readjustment

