Simulation suggests that a baseline covariate which is associated with the outcome variable could modestly reduce the sample size needed for 80% power (simulation results are available upon request). Sample size readjustment based on baseline predictors will be considered, subject to approval by the DSMB. The guiding principle is (CHMP, Reflection Paper on methodological issues in confirmatory clinical trials planned with an adaptive design, 2007): Analysis methods that control the type I error must be pre-specified. Whenever possible, methods for blinded sample size reassessment that properly control the type I error should be used, especially if the sole aim of the interim analysis is the re-calculation of sample size.

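### The primary model adjusts for site only; prespecifying prognostic baseline covariates that are already collected would add roughly 1 to 6 points of power at N = 216, under assumed covariate strengths

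*Combined protocol and SAP*

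**What the plan says.** SAP 3.2.2 (Specific Aim 1, Primary Analysis) states: "The primary analysis is a logistic regression with treatment arm as a predictor". Site enters as a random intercept, the treatment coefficient is tested by a one-degree-of-freedom likelihood ratio test, and the p-value comes from permutation under the block randomization. "The hypothesis test is to be two-sided with alpha of 0.05". The further models (a) to (d) vary only site, country and their interactions with drug. Age and gender appear in additional analyses, and anatomic location in the subgroup model.

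SAP 3.4.1 sets 216 patients, "which we anticipate will provide approximately 80% power to detect a difference of 20% in the proportion" achieving control at six months. Under its sample size readjustment heading it adds: "Simulation suggests that a baseline covariate which is associated with the outcome variable could modestly reduce the sample size needed for 80% power". It continues: "Sample size readjustment based on baseline predictors will be considered, subject to approval by the DSMB". It names no covariate, gives no size or rule for a change, and does not say whether the covariate would enter the primary test. It does cite the principle that methods controlling type I error be fixed in advance.

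Other outcomes are treated differently. In SAP 3.2.2, quality of life (item 5), macular thickness (item 9) and vitreous haze (item 12) are each modelled with the baseline value as a covariate. SAP 3.4.2 counts that benefit for quality of life and notes it for macular thickness.

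**The concern.** A smaller sample for the same power and more power for the same sample are the same gain, and both require the covariate to be in the test. The SAP recognises the gain for the primary endpoint but leaves such covariates out of the primary model, and gives no reason.

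The natural candidates are at hand. Success is defined by anterior chamber cell and vitreous haze grades (protocol Table 2), and the same grades are recorded at the baseline eye examination. Anatomic location by history is already the prespecified subgroup factor, and it is listed with prior inflammation assessments among the imputation covariates (SAP 3.5).

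At stake are a few points of power in a design that meets its target without spare margin. There is also an open link: the readjustment clause refers to baseline predictors that the test as specified does not use.

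**Working it through.** **Inputs.** Success 0.4 on methotrexate and 0.6 on mycophenolate mofetil, two-sided alpha 0.05, 80% power (SAP 3.4.1). "We assume 10% will be lost to follow-up in the first six months" (same section). 108 per arm, so 108 × 0.9 = 97.2 evaluable per arm.

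**Reproducing 216.** SAP Equation (5): 2N = 4 × (1.960 + 0.842)² × 0.5 × 0.5 / 0.2² = 196.2 evaluable. Dividing by 0.9 gives 218.0; multiplying by 1.1 gives 215.8. The two-proportion formula with separate variances under the alternative gives n = [1.960 × √0.50 + 0.842 × √0.48]² / 0.04 = 96.9, so 97 per arm. Then 97 / 0.9 = 107.8, so 108 per arm and 216 in total. The stated figure reproduces.

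**Power at 216 without a covariate.** Equation (5) solved for power: Φ(0.2 / √(0.5 / 97.2) − 1.960) = 79.6%. The second formula gives 80.0% at 97 per arm. The stated approximate 80% is met. The small critical-value adjustment for the interim looks is left out throughout.

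**Gain from a covariate, N kept at 216.** Likelihood ratio tests from logistic models were simulated with 97 per arm, marginal success rates held at 40% and 60%, 4,000 replicates per row and no site effect. Monte Carlo error is about √(0.8 × 0.2 / 4000) = 0.6 points per figure. Covariate strength is an assumption.

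| Assumed covariate | With covariate | Without | Gain (points) |
|---|---|---|---|
| Binary 50/50, odds ratio 2 | 81.4% | 80.3% | 1.1 |
| Binary 50/50, odds ratio 3 | 82.5% | 80.5% | 2.0 |
| Binary 50/50, odds ratio 4 | 84.9% | 81.4% | 3.5 |
| Score, SD 0.7 on logit scale | 83.9% | 80.5% | 3.4 |
| Score, SD 1.0 on logit scale | 86.4% | 80.1% | 6.3 |

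A separate simulation with one standard normal covariate agrees: 84.0% v 80.7% at an odds ratio of 2.12 per SD, and 86.3% v 79.9% at 2.72 per SD. A weak covariate (1.35 per SD) gives 80.7% v 80.1%.

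**Cost if the covariates are useless.** Three covariates unrelated to outcome: power 80.5% with them, 80.8% without; type I error 5.3% v 5.4%. If one of the three is prognostic with SD 0.7, power is 83.0% v 79.9%.

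**Illustration of a cut with the model unchanged.** The cut sizes are chosen here; the SAP gives none.

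| Cut | N | Evaluable per arm | Equation (5) | Second formula |
|---|---|---|---|---|
| None | 216 | 97.2 | 79.6% | 80.1% |
| 5% | 205 | 92.25 | 77.5% | 78.0% |
| 10% | 194 | 87.3 | 75.3% | 75.7% |

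If the covariate is in the test, a proportionate cut does hold power. With a covariate explaining about 11% of within-arm outcome variance and N = 193, simulated power is 81.3% with it and 77.7% without.

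**The case against.** The choice is defensible. Randomization is blocked within site, and the primary model accounts for that factor. The test is valid and reaches its stated power. All of this stands, and it is why the point concerns efficiency and not an error.

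The size of the gain is assumed. No document reports how strongly anatomic location or baseline grades predict success, and eligibility requires active inflammation, which narrows the range of baseline grades. A binary factor with odds ratio 2 gains only about one point. The simulation also omits the site effect and does not use the permutation p-value. These limits stand, so the gain should be read as a range.

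Vitreous haze may be impossible to judge, or less reliable, with media opacity (protocol 5.3.2, SAP 3.2.1), and some eyes are only partly assessable. This is largely answered: SAP 3.1 requires every patient to have at least one fully assessable eye meeting the severity criteria, so a worst-assessable-eye grade can be defined for all. Noise in a baseline covariate reduces the gain but does not invalidate the test, because eligibility is verified on the baseline grades before randomization.

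Timing is a fair objection. The interim analyses use the final model (SAP 3.10) and are run unmasked by the principal statistician (SAP 3.10.2). Enrollment began in August 2013, and the last logged SAP revision is 9 March 2017. The documents do not show whether an interim look had taken place by then.

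A reader might infer that the SAP plans to cut the sample size of an unadjusted test and so lose power. The documents do not support that. Readjustment is only to be considered, with DSMB approval; no cut, covariate or rule is given; N is 216 throughout; nothing says the test would stay without the covariate after a readjustment; and the test is adjusted for site.

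**Conclusion.** The point holds as an available improvement. The primary model has no patient-level prognostic covariate, although the SAP acknowledges the efficiency gain and adjusts several secondary outcomes for baseline. Adding covariates already collected would raise power from about 80% by roughly 1 to 6 points at N = 216. That range rests on assumed strengths (binary odds ratio 2 to 4, or a score with SD 0.7 to 1.0 on the logit scale), 40% v 60% success and 10% loss. If the covariates are uninformative, the loss is about 0.3 points, within simulation error.

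The readjustment clause needs one clarifying sentence. It does not amount to a planned loss of power, and 79.6% by Equation (5) is rounding around the stated 80%, not a shortfall.

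**What to change.** In SAP 3.2.2, before any further unmasked analysis:

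- Add to the primary model, alongside arm and the site random effect, anatomic location by history (two categories, as in the subgroup analysis) and the baseline anterior chamber cell and vitreous haze grades in the worst assessable eye. State how the grade is taken when one eye cannot be assessed for that field.
- Keep the permutation p-value under the block randomization, computed from this model. It stays valid because the covariates precede randomization.
- Report the arm-plus-site model as supportive. The adjusted odds ratio is conditional on the covariates, so the two estimates are not expected to coincide.

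In SAP 3.4.1, keep N = 216 and state that covariate-based readjustment is allowed only for covariates named in the primary test.

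The cost is SAP text and one rule for unassessable fields; no new data are needed. Because the interim looks share the primary model, the list should be fixed by people who have not seen outcomes by arm, and the revision history should record whether any interim look came before the change.

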2.4 Randomization

2.4.1 Stratification between sites

Patients will be recruited from nine sites: [REDACTED]

[REDACTED] (see Manual of Operations Section 2.2 for details). Patients will be randomized to two treatments (arms): methotrexate (X) or mycophenolate mofetil (Y). The treatment protocols are specified in the FAST Uveitis Trial Manual of Operations.

Within each site, assignments will be conducted using a block randomization scheme with randomly varying block sizes.

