- Baseline best spectacle-corrected visual acuity, vitreous haze, macular thickness
- Vasculitis

Inclusion of Data

- Data will be included for all outcomes within the window period of -2 weeks to +4 weeks around the 6 Month Visit date for Phase I (0-6 months).
- Data will be included for all outcomes within the window period of -2 weeks to +4 weeks around the 12 Month Visit date for Phase I (6-12 months).
- Data will be included for all outcomes within the window period of -2 weeks to +4 weeks around the 6 Month Visit for Phase II (0-6 months).

3.2.2 Specific Aim 1

Primary Analysis.

The primary analysis will be a logistic regression model, predicting treatment success at 6 months based on treatment arm. We wish to aggregate sites within countries, and countries within treatments provided we find no evidence of heterogeneity of sites or countries.

Specifically, the pre-specified primary analysis will be performed as follows. We denote the assignment group of patient i , $i=1, \dots, N$ (where N is the number of subjects) by X_p^1 which equals 0 when the patient is in the methotrexate group and 1 when the patient is in the mycophenolate mofetil group. The outcome variable is Y_p which is 1 if treatment success of patient i is achieved by six months, and 0 otherwise. The variable is missing if the patient is lost to follow-up or drops out of the study for reasons other than discontinuation due to intolerance or adverse events; if the patient discontinues the medication due to intolerance or adverse events such as abnormal laboratory findings, the value is 0.

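### The SAP commits to the pooled treatment estimate and confidence interval only when no site or country interaction is found; the primary test itself is unconditional, but the estimate that goes with it is not secured

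*Combined protocol and SAP*

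**What the plan says.** The Primary Analysis part of SAP 3.2.2 opens with an intention: "We wish to aggregate sites within countries, and countries within treatments provided we find no evidence of heterogeneity of sites or countries". It then fixes one primary model, a logistic regression on treatment arm with a random intercept for site and no interaction term. The null hypothesis for treatment is "tested using a likelihood ratio test with one degree of freedom", two-sided at 0.05, with the P-value obtained by permutation under the block randomization.

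Supplementary models with site and country interactions follow, and after them the reporting rule. If neither interaction is in evidence, the sentence ends: "country interaction, we will report pooled treatment effects and confidence intervals". If sites differ: "In the event evidence suggests a difference between treatment sites, we will report treatment effects by site, and repeat the analysis excluding particular sites". For countries, a treatment-by-country "interaction will lead us to report treatment effects and confidence intervals by country".

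Three other places bear on this:
- SAP 2.4.1: "Patients will be recruited from nine sites". SAP 3.2.2 pools sites or countries that have fewer than three observations.
- SAP 3.6, on pooling across sites, says that about three-fourths of patients should come from one hospital network. It gives no pooling rule.
- SAP 3.2.2, planned secondary analysis 16, sets a 10% non-inferiority margin, judged on a 95% confidence interval if the primary comparison shows no difference.

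**The concern.** The trial is sized for one pooled comparison. A reporting rule that turns on an interaction pre-test makes the promise of the powered estimate depend on a test for which the trial was not sized. By-site results, which take over in the site branch, are too imprecise to stand in for it. Two interactions are examined, so chance has two opportunities to trigger the rule, and nothing defines how strong the evidence must be.

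The choice of sites to leave out is also open, and it would be made after site results have been seen.

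The section pulls in two directions. It advises against interaction terms in the primary model because they cost power, yet it lets the same interactions decide whether the pooled effect and interval are promised. The non-inferiority reading needs an overall interval, and analysis 16 does not say what is used when the condition for pooling fails.

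**Working it through.** **1. The plan's own figure.** Inputs from SAP 3.4.1: success 0.40 v 0.60, two-sided alpha 0.05, power 80%, 10% loss. Equation (5) gives 2N = 4 × (1.960 + 0.842)² × 0.5 × 0.5 / 0.20² = 196.2 evaluable. With 10% loss this is 196.2 × 1.1 = 215.8, or 196.2 / 0.9 = 218.0. The stated 216 is reproduced. With 108 × 0.9 ≈ 97 evaluable per arm, power is 0.80. This is the power of the pooled comparison.

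**2. How often the condition fails by chance.** The SAP gives no interaction test, level or site sizes, so all three are assumed. Two independent, calibrated tests at level a give 1 − (1 − a)²: 9.75% at 0.05, 19% at 0.10 and 36% at 0.20.

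Simulation: 20,000 trials per layout, about 97 evaluable per arm, nine sites, two countries, 40% v 60% at every site. The tests were an 8-df treatment-by-site and a 1-df treatment-by-country likelihood ratio test with asymptotic P-values and fixed site intercepts. In the unequal layouts the large sites form one country.

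| Assumed layout | Site, 5% | Country, 5% | Either, 5% | Either, 10% |
|---|---|---|---|---|
| Nine equal sites | 8.3% | 6.0% | 12.6% | 22.1% |
| Three large, six small | 13.4% | 7.1% | 17.7% | 29.7% |
| Two large, seven graded | 16.0% | 7.2% | 20.2% | 33.3% |
| Two large, seven small | 16.8% | 7.4% | 21.0% | 33.9% |

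The 8-df test rejects too often when sites are small. In a further layout (evaluable patients per site 60, 50, 36, 12, 10, 8, 7, 6, 5; total 194) the asymptotic tests triggered in 18.6% of trials. With critical values set so that each test truly has 5%, this fell to 9.1%. The range at an assumed 5% level is therefore about 9% to 21%.

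**3. How well the condition detects real heterogeneity.** With a true difference of 25 points in one country and 5 in the other, the country test is positive in about 22% of trials at 0.05 and about 32% at 0.10. The condition fires by chance and usually misses a large real difference.

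**4. Precision of what would be reported instead.** The 95% half-width for a difference is 1.96 × √(2 × 0.24 / n), with n per arm:
- pooled, n = 97: ±14 points
- n = 37 (a large site): ±22 points
- n = 11 (equal sites): ±41 points
- n = 4 (a small site): ±68 points

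For the country branch, SAP 6.2.3 projects 15 US patients at one third of enrolment. That is 15 × 3 = 45 in all, about 45 × 0.9 / 2 ≈ 20 evaluable per arm, and ±30 points. With the same benefit everywhere, at least one site points the wrong way in 69–76% of simulated trials.

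**5. Choosing sites to exclude.** With no treatment effect, the smallest P-value over the full analysis and all leave-one-site-out reruns is below 0.05 in 14–15% of trials. If reruns are tried only after a positive interaction test at 5%, the figure is 7–9%. The full analysis alone gives 5.1–5.7%. The excess arises only if a rerun is taken as the conclusion.

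**The case against.** The strongest reply is that the trial's main answer is not conditional at all. SAP 2.3.1 defines the primary outcome as the difference in success proportions, without qualification. The model, the 1-df test, the permutation P-value and the alpha in SAP 3.2.2 do not depend on an interaction result. This stands. A reader might infer that a pre-test could replace the primary test; the documents do not support that.

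The SAP also never says that the pooled estimate is withheld when interaction is found. It promises the estimate under a condition and is silent otherwise, and repeating an analysis without some sites implies that the original was done. The authors may always have meant to report it. The reply is fair, but no other sentence says so: SAP 3.6 gives no rule, and the country-and-site item among the secondary analyses refers back to the same text.

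Third, 3.2.2 undertakes, under Planned Secondary Analyses, to keep the one prespecified test apart from supplemental tests and to label exploratory work. That guards against a site-exclusion rerun passing as the primary test, so the 7–15% error rates are not a property of the plan. It does not secure the pooled estimate or interval.

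Fourth, a reader might infer that nine separate site results would follow, or that one trial in six would lose its estimate. Nine is a ceiling: very small sites are pooled, and a country interaction leads to by-country results only. No single trigger rate can be given, and roughly half of an 18–19% figure comes from using an asymptotic test that the SAP does not name.

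**Conclusion.** The point holds in a limited form. As written, the SAP commits to the pooled effect and interval only if an undefined interaction check is negative, and it leaves the choice of excluded sites to be made after the data are seen. Exposed are the pooled estimate and interval, and with them the interval for the non-inferiority reading. The type I error and power of the primary test are not affected.

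With no true heterogeneity, the condition would fail by chance in about 9% to 21% of trials at an assumed 5% level per test. With asymptotic tests at an assumed 10% level the range is 22–34%. These figures depend on the assumed test, level and site sizes, and on treating the SAP's unquantified evidence as an automatic trigger. The gap in the text does not depend on them. It should be closed, because the substitute results are far less precise than the pooled one and the correction is nearly free.

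**What to change.** Amend the Primary Analysis part of SAP 3.2.2 to say:
- The pooled treatment effect and confidence interval from the random-intercept model are reported in every case, as the primary result. The non-inferiority reading uses the pooled interval.
- Interaction tests and by-site and by-country effects are supportive checks of consistency, reported with their P-values and intervals.
- Analyses that leave out sites are sensitivity or exploratory analyses. Preferably each site is left out in turn, so that none is chosen from the data.

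The opening wish to aggregate only "provided we find no evidence of heterogeneity of sites or countries" should be reworded to match. The cost is a few sentences. No planned analysis is removed, and the 216 patients, the alpha and the power are unchanged.

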categories: anterior/intermediate or intermediate only, and posterior/panuveitis). Anatomical location by history is considered the prespecified analysis; anatomical location at enrollment will supplement this finding.

We propose to proceed as follows. We propose to begin with Equation (1), adding terms $\beta_3 X_i^3 + \beta_{13} X_i^1 X_i^3$ for anatomic location and for treatment-location interaction. We wish to test the hypothesis that $\beta_{13} = 0$, i.e. that there is a difference in treatment efficacy between the anatomic locations, controlling for country. Alternative models will be fit in which the country, site, and treatment x country terms are omitted.

We will also report relative risks in each substratum, using relative risk regression.

Additional analyses will add gender and age to the predictors. The entire analysis will be repeated for each gender, and separately for each country (US and India) and anatomic location.

Planned Secondary Analyses.

Each of the following secondary analyses is designed to test the hypothesis that treatment assignment affects a given outcome, after controlling for selected covariates. All analyses will be repeated without controlling for covariates (i.e., using treatment assignment as the only predictor). In all cases, appropriate regression diagnostics and/or goodness of fit tests will be performed (further details are given below). In addition, we will compute jackknife influence statistics in each analysis, to determine whether or not any single observation (eyes or patients, as appropriate) have an undue effect on the final conclusion. All models with site effects will be repeated omitting this effect, and again repeated including a treatment-site effect, and with country and/or treatment by country interactions (i.e., pooling within countries when appropriate). When reporting findings, care will be taken to distinguish the single prespecified test from supplemental tests (whether prespecified or unprespecified); exploratory analyses will always be labeled as such. All alpha levels are to be two-sided.

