1. *Twelve-month endpoint for successes.* We propose to compare the proportion who maintain successful control for twelve months (i.e. the outcome is the proportion who have achieved control in all study eyes both at the six month visit and at the 12 month visit) between the two study arms. Per protocol, patients with successful control of their inflammation at 6 months remain on the same treatment until 12 months. We will use the same statistical model (and Wald procedure) as for the primary analysis. We test the hypothesis that the coefficients for treatment assignment and treatment assignment/anatomic location interaction both equal zero.

2. *Time to corticosteroid sparing control of inflammation.* We propose to use a Cox proportional hazard model with the outcome being the time to (1) first steroid-sparing control, and separately (2) first control of inflammation, with treatment assignment (and interaction) as the predictors. Time to first steroid-sparing control is the principal prespecified analysis here; alternative approaches will be conducted for additional insight and as sensitivity analyses. We will supplement this analysis with a parametric survival analysis using the Weibull distribution and also with a gamma distribution (note that individuals may drop out at any time, not just at the monthly visits), and with a method treating the time to success as interval censored. The outcome for this analysis is a single number for each patient (not for each eye). The primary statistical

result will be the Wald test for the treatment assignment coefficient. We will repeat the analysis using study site as a fixed effect in this model (and as a sensitivity analysis, will explore random-effects survival analytic methods which are becoming available, see Pankratz et al.).⁶ In supplementary analyses we will include age and anatomic location as additional covariates.

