3.4.2 Power for Subgroup Analyses and Other Analyses

Subgroups in Specific Aim 1.

The prespecified subgroup analysis for specific aim 1 is to examine the difference between the methotrexate and mycophenolate mofetil groups within each anatomic location. Using Equation (5), we anticipate having in excess of 80% power to detect a difference of 25% in success rates.

The power for selected secondary outcomes is provided here.

Secondary Outcomes in Specific Aim 1.

1. *Twelve-month endpoint for success.* We assume an additional loss of 5% between 6 and 12 months (that is, in addition to the 10% already lost to follow-up in the first six months). **We expect approximately 78% power to detect a 20% difference in success rates at the 12-month endpoint.**

2. *Time to corticosteroid sparing control of inflammation.* For sample size planning, we use the approximate formula given in Friedman et al (2010) for the number in each group:

$$N = \frac{(Z_\alpha + Z_\beta)^2 (\phi(\lambda_C) + \phi(\lambda_I))}{(\lambda_I - \lambda_C)^2}$$

where λ_C is the hazard in the methotrexate group, λ_I is the hazard in the mycophenolate mofetil group, and $\phi(u) = \frac{u^2}{1 - e^{-uT}}$

where T is the censoring time (6 months). Previous studies suggest a median success time of approximately 3.5 months for mycophenolate mofetil.¹² **Assuming a 10% loss to follow-up, 108 subjects in each group provides 80% power to detect a difference of 2.47 months in the expected difference.** (Note: λ_C is $\log(2)/3.5$ mo. for this calculation.) We assume an alpha of 0.05 (two sided).

3. *Change in BSCVA.* For sample size planning, we assume a T-test comparing change scores between the two drugs, assuming a standard deviation of the change in visual acuity of 6.5 letters.^{13, 14} The sample size of 108 will provide approximately 80% power to detect 2.63 letters of difference in the change score. In other words, **we expect to have 80% power to detect whether mycophenolate mofetil yields 2.63 letters more of improvement than methotrexate, and we will have greater power to detect greater differences.** The power formula is provided in Chow et al and is computationally implemented in R in the function `power.t.test` (which we used).¹⁵

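### The twelve-month analysis is said to use the primary model but names a joint two-parameter test, and the stated 78% power belongs to a one-parameter comparison

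*Combined protocol and SAP*

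**What the plan says.** SAP 3.2.2, Planned Secondary Analyses, item 1, compares the arms on the proportion with control at both month 6 and month 12. On method it says: "We will use the same statistical model (and Wald procedure) as for the primary analysis". The next sentence reads: "We test the hypothesis that the coefficients for treatment assignment and treatment assignment/anatomic location interaction both equal zero".

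The primary analysis, earlier in SAP 3.2.2, is described differently. "The primary analysis is a logistic regression with treatment arm as a predictor", with study site as a random intercept. The null is a zero treatment coefficient, "which will be tested using a likelihood ratio test with one degree of freedom". On inference: "We propose to compute the P-value by permutation testing, based on the block randomization scheme". No anatomic term and no Wald test appear there.

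Anatomic location enters under the Prespecified Subgroup Analysis, where terms are added "for anatomic location and for treatment-location interaction" and the interaction coefficient is tested alone.

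On power, SAP 3.4.2 assumes a further 5% loss after the 10% lost by month 6 and states: "We expect approximately 78% power to detect a 20% difference in success rates at the 12-month endpoint". It mentions neither an interaction nor a second degree of freedom.

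**The concern.** An analyst cannot follow both sentences of item 1. The interaction coefficient is not in the primary model, so either the model or the hypothesis has to change.

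The choice matters in two ways. First, a joint test spends a second degree of freedom; if the drug effect is the same in every location, that costs power and the stated figure no longer describes the named test. Second, the item sets out to compare two drugs, but a joint null can be rejected because of the interaction alone. A significant result would then not say that one drug maintains control better overall.

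**Working it through.** **Inputs**
- 108 per arm (SAP 3.4.1); two-sided alpha 0.05 (SAP 3.2.2).
- Completers at twelve months: 108 × 0.85 = 91.8, or 108 × 0.90 × 0.95 = 92.34 per arm (losses from SAP 3.4.2).
- Success rates 0.40 and 0.60 (SAP 3.4.1). These are month-6 planning rates. Using them at month 12 is an assumption.

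**Reproducing the stated figure (1 df).** The noncentrality is λ = nδ²/V, with δ = 0.20 and V = 2 × 0.5 × 0.5 = 0.50 (pooled) or V = 0.24 + 0.24 = 0.48 (unpooled).
- Pooled: 91.8 × 0.04/0.50 = 7.34; 92.34 × 0.04/0.50 = 7.39.
- Unpooled: 91.8 × 0.04/0.48 = 7.65; 92.34 × 0.04/0.48 = 7.70.
- Power = Pr[χ²₁(λ) > 3.841] = 77.3-77.6% pooled and 79.0-79.2% unpooled. The usual formula with pooled variance under the null and unpooled under the alternative gives 77.8-78.0%.

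The SAP's 78% is therefore correct for a one-parameter comparison.

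**The test as named (2 df).** If rates and effect are the same in every location, the interaction adds a degree of freedom but no noncentrality, so λ is unchanged.
- Power = Pr[χ²₂(λ) > 5.991] = 67.8-68.1% pooled and 69.7-70.0% unpooled. Computing λ from the log odds ratio gives about 67%.
- Simulation of the arm-by-location logistic model (92 per arm; posterior/pan share 30%, 50% or 70%; 100,000 runs each) gave 67.8-68.2% for the joint test and 77.1% for the one-parameter Wald test.

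**Dependence on the assumed rates** (20-point difference, uniform effect, pooled to unpooled variance):

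| Rates | 1 df | 2 df | Loss in points |
|---|---|---|---|
| 0.40 / 0.60 | 77-79% | 68-70% | 9-10 |
| 0.30 / 0.50 | 79-81% | 70-72% | 9 |
| 0.20 / 0.40 | 84-86% | 76-78% | 8 |
| 0.15 / 0.35 | 88-90% | 81-83% | 7 |
| 0.10 / 0.30 | 92-94% | 87-89% | 5-6 |

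The table is symmetric about 0.5, so 0.50/0.70 matches 0.30/0.50, and so on.

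**Dependence on a uniform effect.** With an assumed 50/50 location split, 92.34 per arm and an average difference of 20 points, joint power is 73% for effects of 15 and 25 points, 82% for 10 and 30, and 97% for 0 and 40.

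**What rejection means.** Take 46 per arm in each of two locations, with 0.40 against 0.60 in opposite directions. The average drug difference is zero, yet λ = 2 × 0.04/(0.48/46) = 7.67 and the joint test rejects about 70% of the time. That is the same rate as for a true uniform 20-point effect.

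**The case against.** Four points can be made for the plan.

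- **A treatment-only analysis is already planned.** SAP 3.2.2 says every secondary analysis will be rerun with treatment as the only predictor. A reader might infer from item 1 that the trial could not say which drug maintains control better. The documents do not support that: the rerun would address it, with about the stated power. What remains is its status. It is labelled a repeat, the joint test is the one named for this endpoint, and the same section promises to keep the single prespecified test distinct from supplemental ones.
- **The joint test could be a gate.** SAP 3.7 uses an overall test before subgroup analysis and extends this to each secondary outcome. That would be a legitimate purpose, but item 1 does not state it or give a follow-up step, and the gate would still lack the quoted power under a uniform effect.
- **Both coefficients might be meant as separate tests.** That does not recover 78%. In the same simulations, the treatment coefficient within the interaction model had about 31-60% power, depending on the location split.
- **The rates are not the SAP's twelve-month rates.** This stands. For a 20-point difference, 0.40/0.60 is the least favourable pair. Because the endpoint requires control at both visits, keeping those rates implies that nobody loses control after month 6. A reader might infer that the joint test can never reach 78%; the table and the heterogeneity figures show that it can.

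The Wald and likelihood ratio difference is minor. For the same hypothesis the two are asymptotically equivalent, and a permutation P-value can be built on either statistic.

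**Conclusion.** The inconsistency is real and is in the current SAP text: item 1 cites a model that lacks one of the two coefficients it tests. The 78% figure is sound arithmetic for a one-parameter comparison and does not belong to the test named. At 0.40/0.60, with about 92 per arm and a uniform effect, the joint test has about 68-70%. The absolute figure depends on twelve-month rates that the SAP does not give. The loss relative to the one-parameter test, about 5 to 10 points over the rates examined, persists as long as the effect is uniform. It shrinks or reverses if the effect differs strongly by location, but a rejection may then reflect the interaction and not an overall drug difference.

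A reader might go further and infer that the trial is undersized or that its main result is in doubt. Neither follows. The sample size rests on the month-6 primary comparison, and this is one secondary endpoint. The point should be corrected before analysis.

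**What to change.** In SAP 3.2.2 item 1, name the one-degree-of-freedom test of the treatment coefficient from the primary model (random site intercept, likelihood ratio statistic, permutation P-value) as the principal twelve-month test. Move the treatment-by-location interaction to a separately labelled supplementary test and correct the Wald wording. The SAP 3.4.2 power statement can then stay, with the assumed twelve-month rates added.

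If the joint test is wanted, write out its model, say which test follows a rejection, and restate its power as about 68-70% under 0.40/0.60 with a uniform effect.

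Either route changes SAP wording only. It needs no additional patients, visits or data.
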